10.2.1. Temporary Interruption of Study Treatment

If the subject requires re-hospitalization (re-hospitalization is defined as a combined total of inpatient and/or ER stay ≥ 24 hours) during the study drug treatment for reasons other than the primary efficacy outcome or bleeding, the subject should be maintained on the study drug at the discretion of the investigator. If the treating physician feels that the subject requires any anticoagulation during the re-hospitalization, study drug needs to be temporarily interrupted, and can be resumed upon hospital discharge. Mechanical methods of prophylaxis may be used during hospitalization. If this method is chosen, study drug may be continued.

In addition, the study drug should be temporarily interrupted if the subject:

- Develops any medical condition that may require use of anticoagulant therapy, thromboprophylaxis, fibrinolysis or poses an increased bleeding risk.
- Undergoes percutaneous coronary intervention, coronary artery bypass graft, any other interventional procedure, that may require use of anticoagulant therapy, thromboprophylaxis, or poses an increased bleeding risk. For temporary interruption of study drug for an elective procedure or surgery, it is suggested that investigators follow measures in [Table 4](#) and [Table 5](#) (Section 10.2.2 Approach to Subjects with Temporary Interruption of Study Treatment).
- Experiences a major bleeding event other than intracranial bleeding. For less severe bleeding events, investigator discretion is allowed. If possible, study drug should be resumed when the bleeding event has resolved and the cause has been identified and corrected.
- If a subject develops a new neurologic deficit or significant alteration in mental status suggesting a cerebral vascular accident. Once a diagnosis is definitively made and appropriate treatment is provided, the study drug may be restarted at the discretion of the investigator.
- Develops a platelet count less than 50,000/ μL . If a repeat platelet count is obtained, and the result indicates that the abnormal platelet count was spurious, study drug may be restarted. If the finding was not spurious, study drug may be restarted after 2 consecutive values greater than 75,000/ μL at least 1 week apart have been obtained.
- Has a serious adverse event that is considered by the investigator to be possibly related to, or exacerbated by, study drug administration.
- Requires a prohibited therapy on a temporary basis (see Section 8, Prestudy and Concomitant Therapy).

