9.2.2. Approach to the Subject with an Efficacy Outcome Event

If a subject has a suspected efficacy outcome event during the study, the treating physician should exercise clinical judgment and follow established guidelines to apply the standard of care. At the treating physician's discretion, the routine measures described below may be considered.

- Temporarily interrupt or permanently discontinue study drug treatment as clinically indicated. Unblinding of study drug should not be necessary, as anticoagulation regimens do not require adjustment regardless of treatment group assigned when study drug is administered in the doses used in this study.
- Perform necessary diagnostic procedures and consider the usual treatment measures for VTE and/or cardiac ischemic events if physical examination and diagnostic testing suggest benefit could be obtained.

After clinical evaluation of the suspected efficacy outcome event is completed restarting study drug may be considered if none of the conditions requiring permanent discontinuation are present (Section [10.2.3](#), Permanent Discontinuation of Study Treatment), and after consultation with the medical monitor. In the event that a decision is made to restart study drug (Section [10.2.1](#), Temporary Interruption of Study Treatment), guidelines for restarting study drug

(Section 10.2.2, Approach to Subjects with Temporary Interruption of Study Treatment) may be followed if applicable based on the clinical judgment of the investigator.

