9.5.2. Approach to the Subject with a Bleeding Event

If a subject has a serious bleeding event during study drug treatment, the following routine measures should be considered:

- Delay the next study drug administration, or discontinue treatment if indicated. Rivaroxaban has a plasma half-life of approximately 5 to 9 hours, and in some subjects up to 13 hours. Therefore, temporary cessation of study drug may allow control of bleeding. Unblinding of study drug should not be necessary. As there is not a specific reversal agent for rivaroxaban, management of the subject should not be impacted by knowledge of study drug treatment.
- Consider the usual treatment measures for bleeding events, including fluid replacement and hemodynamic support, blood transfusion, and fresh frozen plasma, if physical examination and laboratory testing suggest benefit could be obtained.
- Consider that other causes besides antithrombotic medication can be contributory to the seriousness of the bleeding event (i.e., rule out disseminated intravascular coagulation,

thrombocytopenia, and other coagulopathies; kidney and liver dysfunction; concomitant medications, etc.), and treat accordingly.

If bleeding cannot be controlled by these measures, consider administration of 1 of the following procoagulants (according to the dosages advised in their respective package inserts).⁴³

- Activated prothrombin complex concentrate
- Prothrombin complex concentrate
- Recombinant factor VIIa (NovoSeven[®])

Any products administered to control bleeding should be entered in the CRF.

Note: Protamine sulfate and vitamin K are not expected to affect the anticoagulant activity of rivaroxaban. There is currently no scientific rationale for benefit, or experience with systemic hemostatics (eg, desmopressin, aprotinin, and epsilon aminocaproic acid).

After resolution of the bleeding event, restarting study drug may be considered based on the clinical judgment of the investigator.

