10.2.3. Permanent Discontinuation of Study Treatment

If a subject must be permanently discontinued from study drug before the end of the double-blind treatment phase, this will not result in automatic withdrawal of the subject from the study, and the subject should continue to be followed for efficacy and safety outcomes (for details see Section 3.1).

A subject should be permanently discontinued from study drug if:

- The investigator believes that for safety reasons (ie, adverse event) it is in the best interest of the subject to stop study drug.
- The subject develops any condition which requires anticoagulation or thromboprophylaxis extending beyond the treatment phase of the study (eg, atrial fibrillation, VTE).
- The subject becomes pregnant.
- The subject has a fall in CrCl to below 20 mL/min or 2 consecutive measurements less than 30 mL/min at least 1 week apart (as calculated by Cockcroft-Gault formula, see Section 9.1.2) during the study.
- The subject requires hemofiltration or dialysis on a permanent basis
- The subject requests to discontinue study drug permanently
- The subject has a hemorrhagic stroke, or intracranial bleeding

If the subject permanently discontinues study drug before Day 45, he/she should be instructed to complete an unscheduled visit and the remaining scheduled visits, including the Day 7 and Day 21 visits (if not yet completed), and Day 45 (+4d) and Day 75 (\pm 5d) visits (Section 9.1.3). The Day 45 visit should be a clinic visit; the Day 75 visit may be a telephone visit.

The eCRF is to be completed to identify the reason for permanent discontinuation of study drug. The investigator will provide a narrative to describe any adverse events that occur up to the Day 75 (\pm 5d) visit. The appropriate adverse event or serious adverse event sections of the eCRF

are to be completed. If study drug is terminated for a serious adverse event, expedited reporting (within 24 hours) is also required as outlined in Section 12.3.2, Serious Adverse Events.

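### Protocol 9.5.2 and the neurologic bullet of 10.2.1 allow discretionary restart of study drug without excepting hemorrhagic stroke or intracranial bleeding, for which 10.2.3 calls for a permanent stop

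*Protocol*

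**What the plan says.** Five places in the protocol and one in the SAP bear on restart after a bleed or a suspected stroke.

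- **Protocol 10.2.3** opens with "A subject should be permanently discontinued from study drug if" and lists, without exception, "The subject has a hemorrhagic stroke, or intracranial bleeding".
- **Protocol 10.2.1, neurologic bullet**, treats as a temporary interruption: "If a subject develops a new neurologic deficit or significant alteration in mental status suggesting a cerebral vascular accident". It then adds: "Once a diagnosis is definitively made and appropriate treatment is provided, the study drug may be restarted at the discretion of the investigator".
- **Protocol 10.2.1, major-bleeding bullet**, applies when the subject "Experiences a major bleeding event other than intracranial bleeding". It says that, where possible, "study drug should be resumed when the bleeding event has resolved and the cause has been identified and corrected".
- **Protocol 9.5.2** covers any serious bleeding event during treatment. Its first measure is to delay the next dose, or to discontinue if indicated. It ends: "After resolution of the bleeding event, restarting study drug may be considered based on the clinical judgment of the investigator".
- **Protocol 9.2.2** covers suspected efficacy events. There, "restarting study drug may be considered if none of the conditions requiring permanent discontinuation are present". It cites 10.2.3 for those conditions and also asks for consultation with the medical monitor.
- **SAP 2.3** counts failure to stop permanently after a hemorrhagic stroke or intracranial bleeding as a key protocol deviation. That removes the subject from the per-protocol set.

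**The concern.** The limit set by 10.2.3 is repeated in some of the texts that sites use to manage an event and is missing from others. The two that lack it are the section written for serious bleeds and the bullet written for suspected strokes, where the limit matters most. The protocol also routes readers to them: the synopsis sends serious bleeds to 9.5.2, and Section 6 sends temporary interruptions to 10.2.1. Neither of those pointers mentions 10.2.3.

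Two things are at stake. The first is safety: a subject with a hemorrhagic stroke or intracranial bleed could be put back on blinded study drug by a site acting in good faith on 9.5.2 or on the neurologic bullet. Protocol 1.1 says that design elements were changed from MAGELLaN specifically to reduce major bleeding. The second is consistency between protocol and analysis plan: the same site action is permitted by one protocol text and scored as a key deviation by the SAP.

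**Working it through.** No plan figure needs to be reproduced and no arithmetic applies. The check is a comparison of texts.

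**Step 1. Do the permissive texts cover the events named in 10.2.3?**
- The neurologic bullet is triggered by a suspected cerebral vascular accident of any type. Protocol Attachment 1 defines stroke as resulting from either hemorrhage or infarction. Once the diagnosis is made and treated, the bullet allows restart whatever the diagnosis was. As written, hemorrhagic stroke is inside it.
- Section 9.5.2 applies to any serious bleeding event and names no excluded site. Section 9.5.1 lists intracranial bleeding as a critical site for ISTH major bleeding. As written, intracranial bleeding is inside 9.5.2.

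**Step 2. Which texts carry the limit?**

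| Text | Covers hemorrhagic stroke or intracranial bleeding? | Excepts it or points to 10.2.3? |
|---|---|---|
| 10.2.3 | Yes, permanent stop | It is the rule |
| 10.2.1, major-bleeding bullet | No, set aside | Yes, by exception |
| 9.2.2 | Yes, while handled as a suspected efficacy event | Yes, by reference, plus medical-monitor consultation |
| 10.2.1, neurologic bullet | Yes | No |
| 9.5.2 | Yes | No |

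The gap is in the last two rows.

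**Step 3. How far does 9.2.2 close it?** Section 9.2.1 requires symptoms compatible with a TIA or stroke to be sent for adjudication as a suspected efficacy event. A site that handles the deficit under 9.2.2 therefore meets the 10.2.3 limit. A site that reads the neurologic bullet alone does not. Nor does a site that treats a confirmed hemorrhage as a bleed under 9.5.2.

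**Step 4. What follows in the analysis?**
- *Primary efficacy.* The ITT set is all randomized subjects with valid consent, analyzed as randomized to Day 45. A restart removes nobody.
- *Per-protocol sensitivity analysis (SAP 5.2.2).* A subject restarted after one of these events is excluded through SAP 2.3.
- *Principal safety outcome.* This is time to first ISTH major bleed. An intracranial bleed is itself a major bleed, so a later restart leaves the comparison essentially unchanged.
- *Multiple-occurrence model for major bleeding (SAP 6.1).* It uses the on-treatment phase, which runs to 2 days after the last dose. A restart lengthens that phase and so can affect whether a repeat bleed is counted.

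**Step 5. Other major bleeds.** For a non-intracranial major bleed, 10.2.1 describes resumption once two things hold: the bleed is over, and its cause has been found and dealt with. Section 9.5.2 mentions only the first, plus judgment. A site could act within 9.5.2 without having met the second element of 10.2.1.

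**The case against.** The strongest reply is that the texts can be obeyed together. The neurologic bullet and 9.5.2 permit restart but do not direct it, while 10.2.3 names the events specifically. A careful reader would let the specific stop rule govern. Section 9.5.2 also opens with the option to discontinue, 9.2.2 already catches a suspected stroke, and the SAP deviation rule shows that 10.2.3 was meant to control.

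Much of this stands. It means that a reader who infers that the protocol positively directs restart after hemorrhagic stroke goes too far. The wording is permissive, and the major-bleeding bullet of 10.2.1 agrees with 10.2.3. What remains is that neither permissive text says it is subject to 10.2.3, although 9.2.2 says exactly that for its own events. A site should not have to work out the precedence.

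On other major bleeds, a reader might infer two incompatible thresholds. The documents do not support that. Section 10.2.1 says when drug should be resumed, where possible; 9.5.2 says when restart may be considered. Neither says that restart is allowed only then, and the scopes (major versus serious) overlap without being identical. This is a difference in wording to be aligned, not a contradiction.

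**Conclusion.** The point holds as a gap between sections. Section 9.5.2, and the neurologic bullet of 10.2.1 read alone, allow discretionary restart after events for which 10.2.3 calls for a permanent stop, and neither refers to it. The conclusion rests on the texts as written and on a site consulting one of those two places without also applying 9.2.2 or 10.2.3.

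Its statistical reach is small: one sensitivity analysis and one supplementary safety model, with the primary ITT analysis unaffected. It is worth correcting because it bears on subject safety and costs little.

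No number of subjects is attached. A reader might be tempted to size it from the MAGELLaN major-bleeding rates in Protocol 1.1.5 (1.1% versus 0.4% over Day 1 to Day 35). Those rates include the active-control phase to Day 10 and count all major bleeds, so they would speak only to the secondary wording difference. The documents give no intracranial bleeding rate, and the point does not depend on one.

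**What to change.** Reconcile Protocol 9.5.2, 10.2.1, 9.2.2 and 10.2.3 with one another and with the key-deviation list in SAP 2.3. One consistent restart or stop rule should apply to each type of bleed, and each section should point to it. In the same edit, align the wording of 10.2.1 and 9.5.2 for non-intracranial major bleeds. Which rule is right is for the sponsor and the Executive Committee to decide; this review takes no view. Notify sites of the reconciled text.

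The cost is a few sentences in an amendment and a site letter, with no new procedures. SAP 2.3 needs a change only if the reconciled rule differs from the one it now assumes.

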10.2.2. Approach to Subjects with Temporary Interruption of Study Treatment

If study drug is temporarily interrupted to allow a procedure to be performed, the routine measures described in [Table 5](#) and [Table 6](#) should be considered:

Table 5: Preoperative Interruption of Rivaroxaban: A Suggested Management Approach (adapted from Spyropoulos and Douketis 2012)

Patient Renal Function	Low Bleeding Risk Surgery ^a (2-3 drug half-lives between last	High Bleeding Risk Surgery ^b (4-5 drug half-lives between last
------------------------	---	--

	dose and surgery)	dose and surgery)
Normal or mild impairment (CrCl \geq 50 mL/min), or moderate (CrCl \geq 30 and $<$ 50 mL/min) impairment	Last dose: 2 days before surgery (skip 1 dose)	Last dose: 3 days before surgery (skip 2 doses)

CrCl, creatinine clearance.

^a aiming for mild-to-moderate residual anticoagulant effect at surgery (<12-25%).

^b aiming for no or minimal residual anticoagulant effect (<3-6%) at surgery.

Table 6: Postoperative Resumption of Rivaroxaban: A Suggested Management Approach

Low Bleeding Risk Surgery	High Bleeding Risk Surgery
resume on evening of or day after surgery (within 24 hours postoperative)	resume 2 to 3 days after surgery (within 48 to 72 hours postoperative)

Spyropoulos, 2012³⁸.

10.2.3. Permanent Discontinuation of Study Treatment

If a subject must be permanently discontinued from study drug before the end of the double-blind treatment phase, this will not result in automatic withdrawal of the subject from the study, and the subject should continue to be followed for efficacy and safety outcomes (for details see Section 3.1).

A subject should be permanently discontinued from study drug if:

- The investigator believes that for safety reasons (ie, adverse event) it is in the best interest of the subject to stop study drug.
- The subject develops any condition which requires anticoagulation or thromboprophylaxis extending beyond the treatment phase of the study (eg, atrial fibrillation, VTE).
- The subject becomes pregnant.
- The subject has a fall in CrCl to below 20 mL/min or 2 consecutive measurements less than 30 mL/min at least 1 week apart (as calculated by Cockcroft-Gault formula, see Section 9.1.2) during the study.
- The subject requires hemofiltration or dialysis on a permanent basis
- The subject requests to discontinue study drug permanently
- The subject has a hemorrhagic stroke, or intracranial bleeding

If the subject permanently discontinues study drug before Day 45, he/she should be instructed to complete an unscheduled visit and the remaining scheduled visits, including the Day 7 and Day 21 visits (if not yet completed), and Day 45 (+4d) and Day 75 (\pm 5d) visits (Section 9.1.3). The Day 45 visit should be a clinic visit; the Day 75 visit may be a telephone visit.

The eCRF is to be completed to identify the reason for permanent discontinuation of study drug. The investigator will provide a narrative to describe any adverse events that occur up to the Day 75 (\pm 5d) visit. The appropriate adverse event or serious adverse event sections of the eCRF

are to be completed. If study drug is terminated for a serious adverse event, expedited reporting (within 24 hours) is also required as outlined in Section 12.3.2, Serious Adverse Events.

10.3. Withdrawal From the Study

A subject will be withdrawn from the study for any of the following reasons:

- Lost to follow-up (only after all means of all subsequent contact, including locator services where permitted by law, up until the Day 75 ($\pm 5d$) visit, have been exhausted, lost to follow-up will be declared).
- Withdrawal of consent (unless specifically refused by the subject, subject contact will be made to obtain vital status and other outcomes at the Day 75 ($\pm 5d$) visit).

If a subject is lost to follow-up, every reasonable effort must be made by the study site personnel to contact the subject and determine the reason for discontinuation/withdrawal. The measures taken to follow up must be documented.

Study drug assigned to the withdrawn subject may not be assigned to another subject. Subjects who withdraw will not be replaced.

If a subject withdraws consent from study or is lost to follow-up, his or her vital status and other outcomes will be collected at the Day 75 ($\pm 5d$) visit either by telephone or in person, or if applicable, by a review of the subject's medical or public records unless this contact is not allowed by local regulations.

11. STATISTICAL METHODS

Statistical analysis will be done by the sponsor or under the authority of the sponsor.

A general description of the statistical methods to be used to analyze the efficacy and safety of the study drug is outlined below. A more detailed SAP, including detailed censoring rules for time to event analyses and imputation rules for missing or partially missing dates, will be provided in a separate document that will be finalized before the first subject is randomized.

Summaries by treatment group using appropriate descriptive statistics will be provided for all study variables including demographic and baseline characteristics. No imputation will be applied, unless specified otherwise in the SAP. Descriptive statistics such as mean, median, standard deviation, minimum, and maximum will be used to summarize continuous variables. Counts and percentages will be used to summarize categorical variables. Kaplan-Meier method will be used to summarize time-to-event variables. Graphical data displays may also be used to summarize the data.

Unless stated otherwise, all statistical tests will be interpreted at a nominal (that is, without adjustment for multiplicity) 2-sided significance level of 0.05 and all CIs at a nominal 2-sided level of 95%.

Adjudicated results on efficacy and safety outcomes will be used for the interim and final analyses.

11.1. Analysis Set and Analysis Phase

Each analysis involves the following 2 aspects: 1) analysis set, specifying the subjects to be included; and 2) analysis phase, specifying the time window within which data will be included. Key analysis sets and analysis phases are defined below.

11.1.1. Analysis Sets

- Intention-to-Treat (ITT) (as in the International Conference on Harmonisation [ICH] E9 guideline): This analysis set consists of all randomized subjects who have a signed valid informed consent.
- Per-Protocol (PP): This analysis set is a subset of the ITT analysis set. Subjects with key protocol deviations will be excluded from the PP analysis set. Key protocol deviations will be defined in the SAP.
- Safety: This analysis set is a subset of the ITT analysis set, consisting of subjects who receive at least 1 dose of study drug.

11.1.2. Analysis Phases

- Up-to-Day-45: This analysis phase includes all data from randomization to Day 45 (inclusive).
- On-Treatment: This analysis phase includes all data from randomization to 2 days after the last dose of the study drug (inclusive).

11.2. Sample Size Determination

This is an event-driven study. The targeted total number of primary efficacy outcome is 161, based on the ITT analysis set and Up-to-Day-45 analysis phase. If a subject has multiple events, only the first is counted towards study size determination.

This targeted total number of events is determined using statistical software East 5.3 based on the primary efficacy analysis (defined later) and the following assumptions:

- 40% relative risk reduction (RRR) in the primary efficacy outcome based on the ITT analysis set and Up-to-Day-45 analysis phase (RRR is defined as 1 minus the hazard ratio (HR) of rivaroxaban versus placebo.)
- Power of 90% assuming the above RRR
- Two-sided significance level of 0.05.

To observe the targeted 161 events, it is estimated that a total of approximately 8,000 subjects will need to be randomized to either rivaroxaban or placebo in 1:1 ratio. This estimate is based on an estimated placebo incidence rate of the primary efficacy outcome of 2.5%. In the event that the actual observed blinded pooled event rate is lower than the assumed rate, more subjects may be enrolled to accumulate additional outcome events. Randomization in this study may be stopped at approximately 12,000 subjects for administrative considerations even if the targeted 161 events have not been observed by then. The total number of VTE-related death events may also be taken into account when deciding to stop randomization.

The above assumptions are based on observations from the MAGELLaN study and the IMPROVE VTE risk score published data.^{10, 11, 31, 25, 26, 37}

Table 7 below additionally shows the approximate numbers of randomized subjects needed to observe 161 events based on several other placebo incidence rates.

Table 7: Approximate Number of Subjects Needed to Observe 161 Events

Placebo Incidence Rate	Number of Subjects
3.0%	6,700
2.75%	7,300
2.5%	8,000
2.25%	9,000
2.0%	10,100

